15.8 MISSING DATE INFORMATION FOR PRIOR OR CONCOMITANT MEDICATIONS

For prior or concomitant medications, including rescue medications, incomplete (ie, partly missing) start dates and/or stop dates will be imputed. When the start date and the stop date are both incomplete for a participant, the start date will be imputed first.

15.8.1 Incomplete Start Date

The following rules will be applied to impute the missing numeric fields for an incomplete prior or concomitant medication start date. If the stop date is complete (or imputed) and the imputed start date is after the stop date, the start date will be imputed using the stop date.

Missing month and day

- If the year of the incomplete start date is the same as the year of the first dose of study treatment, the month and day of the first dose of study treatment will be assigned to the missing fields
- If the year of the incomplete start date is before the year of the first dose of study treatment, *December 31* will be assigned to the missing fields
- If the year of the incomplete start date is after the year of the first dose of study treatment, *January 1* will be assigned to the missing fields

Missing month only

- If only the month is missing, the day will be treated as missing and both the month and the day will be replaced according to the above procedure

Missing day only

- If the month and year of the incomplete start date are the same as the month and year of the first dose of study treatment, the day of the first dose of study treatment will be assigned to the missing day
- If either the year of the incomplete start date is before the year of the date of the first dose of study treatment or if both years are the same but the month of the incomplete start date is before the month of the date of the first dose of study treatment, the last day of the month will be assigned to the missing day.

- If either the year of the incomplete start date is after the year of the date of the first dose of study treatment or if both years are the same but the month of the incomplete start date is after the month of the date of the first dose of study treatment, the first day of the month will be assigned to the missing day

15.8.2 Incomplete Stop Date

The following rules will be applied to impute the missing numeric fields for an incomplete prior or concomitant medication stop date. If the date of the last dose of study treatment is missing, impute it as described in Section 15.4. If the imputed stop date is before the start date (imputed or nonimputed start date), the imputed stop date will be equal to the start date.

Missing month and day

- If the year of the incomplete stop date is the same as the year of the last dose of study treatment, the month and day of the last dose of study treatment will be assigned to the missing fields
- If the year of the incomplete stop date is before the year of the last dose of study treatment, *December 31* will be assigned to the missing fields
- If the year of the incomplete stop date is after the year of the last dose of study treatment, *January 1* will be assigned to the missing fields

Missing month only

- If only the month is missing, the day will be treated as missing and both the month and the day will be replaced according to the above procedure

Missing day only

- If the month and year of the incomplete stop date are the same as the month and year of the last dose of study treatment, the day of the last dose of study treatment will be assigned to the missing day
- If either the year of the incomplete stop date is before the year of the date of the last dose of study treatment or if both years are the same but the month of the incomplete stop date is before the month of the date of the last dose of study treatment, the last day of the month will be assigned to the missing day

- If either the year of the incomplete stop date is after the year of the date of the last dose of study treatment or if both years are the same but the month of the incomplete stop date is after the month of the date of the last dose of study treatment, the first day of the month will be assigned to the missing day

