These significant protocol deviations will be reviewed and documented before database lock and unblinding of treatment codes.

7.0 **DEMOGRAPHICS AND OTHER BASELINE CHARACTERISTICS**

Demographic parameters (eg, age, race, sex, ethnicity), baseline characteristics (weight, height, body mass index, ADT failure category, Country, ADT failure category by Country) will be summarized by treatment group for the safety and mITT populations, and baseline efficacy variables will be summarized by treatment group for the mITT population. Continuous variables will be summarized by number of participants and mean, SD, median, minimum, and maximum values. Categorical variables will be summarized by number and percentage of participants.

The ADT failure category based on eCRF will be considered primary data on ADT failure and will be used in all the statistical models rather than the one based on IWRS.

Abnormalities in participants' medical and surgical histories will be coded using the *Medical Dictionary for Regulatory Activities*, version 24.0. The number and percentage of participants with abnormalities in medical and surgical histories in each system organ class and preferred term will be summarized by treatment group for the Safety Population. Psychiatric history, non-drug psychiatric treatment, history of ocular events of special interest will be summarized by treatment group for the Safety Population.

Prior medication is defined as any medication taken before the date of the first dose of DB IP. *Concomitant medication* is defined as any medication taken on or after the date of the first dose of investigational product, and will be summarized for both double-blind treatment period and safety follow-up period.

The March 2017 version of the World Health Organization (WHO) Drug Dictionary Enhanced will be used to classify prior and concomitant medications by therapeutic class. The number and percentage of participants with prior and concomitant drug use will be summarized by treatment group and Anatomical Therapeutic Chemical 4 code for the safety population. Multiple drug use by a participant in the same category will be counted only once in the summary tables.

Rescue medications will be summarized by treatment group and generic terms for the following rescue medication categories in the safety population:

- Insomnia
- Extrapramidal symptoms (EPS) or akathisia
- Agitation, restlessness, and hostility

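### SAP 15.8.1 and 15.8.2 correct the same pair of partial medication dates in opposite directions; for one date pattern, the rule that takes effect tabulates a drug stopped before dosing as concomitant

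*SAP*

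**What the plan says.** SAP 15.8 fixes the order of work: "When the start date and the stop date are both incomplete for a participant, the start date will be imputed first".

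SAP 15.8.1 covers the start date. If only the year is known and it is the year of first dose, "the month and day of the first dose of study treatment will be assigned to the missing fields". For an earlier year: "If the year of the incomplete start date is before the year of the first dose of study treatment, *December 31* will be assigned". It also has a rule for conflicts: "If the stop date is complete (or imputed) and the imputed start date is after the stop date, the start date will be imputed" from the stop date, so the start moves back.

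SAP 15.8.2 covers the stop date. If the year and month are known and "the month of the incomplete stop date is before the month of the date of the last dose of study treatment, the last day" in that recorded month is used. Its own rule for conflicts is "If the imputed stop date is before the start date (imputed or nonimputed start date), the imputed stop date will be equal to" that start, so the stop moves forward.

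SAP 7.0 defines the two classes. A prior medication "is defined as any medication taken before the date of the first dose of DB IP". A concomitant medication "is defined as any medication taken on or after the date of the first dose of investigational product".

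**The concern.** A conflict rule should let what was recorded limit what was invented. In the pattern at issue the stop month is recorded and the start month is not, yet 15.8.2 keeps the invented start and discards the recorded stop. The record then says the opposite of what the site entered.

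The records most exposed are histories of earlier treatment, where partial dates are to be expected. Protocol 4.3 admits patients with a current episode of at least 8 weeks and less than 24 months and an inadequate response to 1 to 3 antidepressants. An earlier course can therefore start and stop within the year of first dose. Inclusion criterion 9 allows one antidepressant at randomisation, and protocol 4.5.2 prohibits most other psychotropics. A misdated record would leave the prior table and appear in the double-blind concomitant table as a second antidepressant or a prohibited drug. In addition, two programmers who each follow the SAP could produce different tables.

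**Working it through.** **Inputs.** The rules are those of SAP 15.8, 15.8.1, 15.8.2 and 7.0. The example dates are assumed, because the documents give none: first dose 15 Sep 2020, last dose 41 days later on 26 Oct 2020.

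**Where the rules meet.** The 15.8.1 rule acts only on an imputed start, and the 15.8.2 rule only on an imputed stop. Both can therefore apply to one record only when both dates are partial. This is also the only case in which the mention of an imputed stop in 15.8.1 can matter.

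**Which one takes effect.** Following 15.8, the start is imputed while no imputed stop yet exists, so the 15.8.1 check has nothing to act on. The stop is imputed next, and 15.8.2 compares it with the start and moves it forward. The dates are then equal, and the 15.8.1 condition is no longer met. The start-first order thus gives the 15.8.2 result and leaves the imputed-stop case of 15.8.1 without effect.

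**Date pairs worked through.**

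| Recorded start | Recorded stop | Imputed start | Imputed stop | If 15.8.2 decides | If 15.8.1 decides |
|---|---|---|---|---|---|
| 2020 | Mar 2020 | 15 Sep 2020 | 31 Mar 2020 | both 15 Sep 2020: concomitant, not prior | both 31 Mar 2020: prior only |
| Feb 2020 | Mar 2020 | 29 Feb 2020 | 31 Mar 2020 | no conflict: prior | same |
| 2019 | Mar 2020 | 31 Dec 2019 | 31 Mar 2020 | no conflict: prior | same |
| 2019 | Mar 2019 | 31 Dec 2019 | 31 Mar 2019 | both 31 Dec 2019: still prior | both 31 Mar 2019: prior |
| Nov 2020 | 2020 | 1 Nov 2020 | 26 Oct 2020 | both 1 Nov 2020: recorded start month kept | both 26 Oct 2020: recorded start month lost |

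The first row is the error. The last row is its mirror image: here 15.8.2 respects the record and 15.8.1 does not. Visit 6 is scheduled for Day 43, which is 15 Sep + 42 days = 27 Oct 2020. The 15.8.1 result would thus move a drug started in November into the double-blind period as SAP 10.0 defines it.

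**How narrow the error is.** I enumerated every pair of partial dates (year only, or year and month; 2018 to 2020) in which the stop is certain to precede the first dose and the start can precede the stop. If 15.8.2 decides, the pairs that become concomitant are:

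- first dose in January: 0 of 375
- March: 2 of 432
- September: 8 of 627
- December: 11 of 738

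All have a year-only start in the first-dose year and a stop in an earlier month of that year. For a first dose in month m there are m − 1 such pairs (3 − 1 = 2, 9 − 1 = 8, 12 − 1 = 11). If 15.8.1 decides, none becomes concomitant. These are counts of date patterns, not of expected patients.

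**The case against.** The best defence is that the SAP already holds the right answer. A programmer who applies 15.8.1 as written, with its mention of an imputed stop, obtains the correct class. It would therefore go too far to say that the SAP plainly orders the wrong one. That stands: the fault is a contradiction whose stated order favours the wrong side.

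A reader might also infer that any medication with two partial dates is misclassified. The documents do not support this. Every other pair in which the stop is certain to precede dosing stays prior.

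Nor is 15.8.2 simply the wrong rule, as the November example shows. Giving 15.8.1 priority for every record with two partial dates would exchange one error for another.

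The consequences are limited too. SAP 7.0 tabulates by ATC 4 code and counts several drugs of one category once. An earlier antidepressant in the same category as the ongoing one therefore changes no count. Background treatment is also described elsewhere: ADT failures and present ADT use from the ATRQ eCRF (SAP 7.0), populations by background ADT (SAP 6.0), ADT compliance (SAP 8.2), and significant deviations reviewed before unblinding (SAP 6.1). No primary, key secondary or adverse-event analysis is specified to use these medication dates. All of this stands and keeps the point minor.

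What remains is that the stated order replaces a recorded month with an invented date and reverses the class. A preference for calling doubtful records concomitant does not justify this, because here the recorded stop leaves no doubt.

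**Conclusion.** The point holds as a minor inconsistency. SAP 15.8.1 and 15.8.2 give opposite corrections when both dates are partial and the imputed stop precedes the imputed start. In the order set by 15.8, a start known only as the first-dose year combined with a stop in an earlier month of that year always yields a concomitant and not a prior medication.

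This rests on 15.8.2 prevailing over 15.8.1, which the start-first sentence implies but the SAP does not state outright. How many records have this pattern cannot be derived from the documents and may be small. A reader might infer that the efficacy results or the whole account of background treatment are in doubt; the documents do not support that, since only the descriptive prior and concomitant medication tables are affected.

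**What to change.** State one precedence rule in SAP 15.8, on the principle that an imputed date never overwrites a recorded month or year. If both dates are partial and the imputed stop is before the imputed start:

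- (a) if the recorded part of the stop date places it before the first dose, set the start to the imputed stop;
- (b) otherwise keep the 15.8.2 rule and set the stop to the imputed start.

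Then limit the conflict sentence in 15.8.1 to a complete stop date and the one in 15.8.2 to a complete start date, with both referring to 15.8 when the two dates are partial.

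Under (a), the record with start 2020 and stop Mar 2020 becomes 31 Mar 2020 for both dates and is prior only. None of the enumerated patterns with a stop certain to precede dosing becomes concomitant. Under (b), the record with start Nov 2020 and stop 2020 keeps its November start.

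The cost is a few sentences in the SAP and a small change to the date-derivation code. No new data are needed.

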15.9 CHARACTER VALUES OF CLINICAL LABORATORY PARAMETERS

If the reported value of a clinical laboratory parameter cannot be used in a statistical summary table because, for example, a character string is reported for a parameter of the numeric type, a coded value must be appropriately determined for use in the statistical analyses. The actual values, however, as reported in the database will be presented in the data listings.

16.0 **COVID-19 RELATED ANALYSES**

To eliminate immediate potential hazards to study participants and site staff due to the COVID-19 pandemic while ensuring participant safety and maintaining data integrity, the Change in Research Memo, followed by COVID-19 global protocol addendum, and protocol amendment #3 were sent to sites during the pandemic.

The following protocol modifications (see protocol amendment #3, Section 12.2) can be followed for active patients who have completed all assessments through Visit 2 (inclusive) per [Table 3-2](#), Schedule of Visits and Procedures. The following procedures apply in cases where patients are either unable or unwilling to attend study visits as a result of the pandemic.

- Allowing wider visit windows when necessary
- Replacing protocol mandated in-person study visits with one or more of the following:
 - o home visits
 - o telemedicine virtual visits (preferred method if/when home visits are not feasible)
 - o telephone/video calls (no recording will be performed)
- Allowing blood draws at alternative or commercial laboratories (where available)
- Study sites shipping investigational products (IP) to research patients (where permissible by local/statutory or country law) and where approved by Sponsor
- Extending the window for consecutive missed doses of IP specifically resulting from COVID-19-related circumstances from 4 or more days to more than 7 days, prior to requiring withdrawal of the patient from the study (see protocol amendment #3, Section 12.2.6.)

This section specifies analyses for evaluating the impact of COVID-19.

16.1 **EFFICACY EVALUATION**

Efficacy Endpoints

For efficacy assessments that are conducted remotely (eg, by telephone, telemedicine virtual visit, video call) or in-home by qualified site staff, the following assessments are required to be completed in the course of the remote visit. Note: The source documents and eCRF should clearly denote which assessments have been completed remotely.

- Montgomery-Åsberg Depression Rating Scale (MADRS)
- Hamilton Anxiety Rating Scale (HAM-A)
- Clinical Global Impression-Severity scale (CGI-S)
- Clinical Global Impression-Improvement scale (CGI-I)
- Hamilton Depression Rating Scale–17 Items (HAMD-17)

To evaluate the impact of COVID-19, the rate of missing due to COVID-19 and assessment done by alternative modalities will be summarized by study visit for each assessment.

For the primary endpoint and key secondary endpoint, one additional sensitivity analysis may be conducted to investigate the impact of COVID-19 dropout cases on the estimation results by treating the dropout cases due to COVID-19 as MAR.

- Participants who discontinued due to lack of efficacy (**but not due to COVID-19**) in the cariprazine arms are assumed to have no treatment effect after the discontinuation. These participants are assumed to copy the profile of placebo arm and missing values are imputed based on the distribution estimated from the placebo group under the MAR using copy-reference approach ([Carpenter et al, 2013](#)).
- The rest of missing values in the placebo arm and cariprazine arms (**including dropouts due to COVID-19**) will be imputed using the observed data in their respective group under the MAR assumption.

In addition, sensitivity analyses for the primary and key secondary endpoints by pre-COVID and post-COVID randomized participants will be performed:

- pre-COVID randomized participants: date of randomization \leq March 11, 2020
- post-COVID randomized participants: date of randomization $>$ March 11, 2020

Lastly, to explore the COVID impact further, the primary analysis for primary and secondary endpoints will be repeated on the subset of participants who completed or discontinued from the study prior to the COVID cutoff date of March 11, 2020.

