8.4.4 Safety Follow-up (Visit 7)

The following procedures will be carried out at the Safety Follow-up Visit (Visit 7/Week 10):

- Review concomitant medications
- Collect vital signs measurements (including weight)
- Collect blood sample for serum pregnancy test (women of childbearing potential only)
- Review and assess AEs and SAEs
- Assess C-SSRS

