3.0 INTRODUCTION

This statistical analysis plan (SAP) provides a more technical and detailed elaboration of the statistical analyses of the efficacy and safety data as outlined and/or specified in the final protocol of Study 3111-302-001 (version dated 23 Jul 2018) and the most recent amendment (amendment 3, dated 27 Jul, 2020). Specifications of tables, figures, and data listings are contained in a separate document. The SAP for pharmacokinetic/pharmacodynamic will be prepared separately.

Study 3111-302-001 is a Phase 3, global, multicenter, randomized, double-blind, placebo-controlled, parallel-group fixed dose study in participants 18 to 65 years of age comparing cariprazine 1.5 mg/day and cariprazine 3 mg/day with placebo as an adjunctive treatment to ongoing ADT in outpatients with a diagnosis of MDD (via the Diagnostic and Statistical Manual of Mental Disorders, Fifth Edition [DSM-5]) who have an inadequate response, as measured by the modified Antidepressant Treatment Response Questionnaire (ATRQ), to 1 to 3 antidepressants administered during the current episode at an adequate dose (as defined per package insert) and duration of ≥ 6 weeks, with at least one dose escalation during the current depressive episode, and have a total score ≥ 22 on the Hamilton Depression Rating Scale-17 items (HAMD-17). Participants, who in the current episode, have had an inadequate response to an ADT taken above the minimum dose (per package insert), and for at least 6 weeks, can be enrolled. The study will consist of up to 14 days of screening and washout of prohibited medications followed by 6 weeks of DB treatment followed by a 4-week safety follow-up. Signed informed consent from the participant or the participant's legally authorized representative will be obtained before any study-related procedures are begun. Participants meeting the inclusion criteria will be randomized (1:1:1 ratio) to 1 of 3 treatment groups (cariprazine 1.5 mg/day +ADT or cariprazine 3 mg/day +ADT or placebo + ADT), stratified by ADT failure category (one ADT failure, more than one ADT failure) and the country.

During the DB treatment period (6 weeks), participants will take 1 capsule of IP, orally, per day in addition to their ongoing ADT as shown in [Table 3-1](#).

The primary analysis will be performed after all participants have completed the 4-week safety follow-up or discontinued from the study and the database has been locked and unblinded.

Table 3-1 Treatment Regimen and Dosing

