Appendix II: Reporting Selected Laboratory Parameters in Conventional Units

All clinical laboratory parameters will be reported in the International System (SI) units as standard practice. In addition, descriptive statistics for values and changes from baseline in conventional units at all assessed visits will be reported for selected laboratory parameters as listed in Table 18-1 below.

Table 18-1 List of Selected Parameters to be Reported in Conventional Units

Number	Laboratory Parameter	Conventional Unit	Decimal Places
1	Alanine Aminotransferase (SGPT)	U/L	0
2	Albumin	G/dL	1
3	Alkaline Phosphatase	U/L	0
4	Aspartate Aminotransferase (SGOT)	U/L	0
5	Bilirubin, Direct (Conjugated)	mg/dL	1
6	Bilirubin, Indirect (Unconjugated)	mg/dL	1
7	Bilirubin, Total	mg/dL	1
8	Blood Urea Nitrogen	mg/dL	0
9	Calcium	mg/dL	1
10	Cholesterol, HDL	mg/dL	0
11	Cholesterol, LDL	mg/dL	0
12	Cholesterol, LDL direct and calculated (combined) (This lab parameter could be the same as #11)	mg/dL	0
13	Cholesterol, Total	mg/dL	0
14	Creatine Kinase	U/L	0
15	Creatinine	mg/dL	1
16	Glucose	mg/dL	0
17	Insulin	uIU/mL	1
18	Triglycerides	mg/dL	0
19	Uric Acid	mg/dL	1
20	Hemoglobin	G/dL	1

Participant narratives will also include the values in conventional units for the selected lab parameters. That might be accomplished by presenting the values in conventional units within the parentheses next to the values in SI units.

Appendix III: SUMMARY OF MAJOR CHANGES FOR SAP AMENDMENT 2

Amendment #2 specifies the following changes to the SAP Amendment #1 for Study 3111-302-001 dated 26 Mar 2021. The major changes are summarized below:

1. Sections 9.2 and 9.3: updated the key secondary efficacy endpoint (from HAM-A to CGI-S at Week 6).
2. Section 16.1: added additional analysis related to COVID-19 impact on primary efficacy endpoint for completed or discontinued patients prior to the COVID-19 pandemic onset, per the FDA feedback.
3. Section 11.0: replaced MMRM by ANCOVA, for consistency with the protocol.
4. Section 7.0: added a clarification that ADT failure based on CRF is primary and will be used for all statistical models, rather than per IWRS.
5. Section 9.3: replaced MMRM by ANCOVA for change from baseline in HAMD-17 total score, per the HAMD-17 data collection at baseline and Week 6.
6. Section 13.0: updated the power that was re-calculated using the mixture parallel gatekeeping procedure.
7. Section 10.2: added a footnote to Tables 10-1 and 10-2 for the parameters with fasting status.

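### The pre-pandemic repeat of the primary analysis selects participants by whether they had finished or dropped out by 11 March 2020; it should select by calendar date

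*SAP*

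**What the plan says.** SAP Section 16.1 ends its efficacy part with an exploratory step: "Lastly, to explore the COVID impact further, the primary analysis for primary and secondary endpoints will be repeated", specifically "repeated on the subset of participants who completed or discontinued from the study prior to the COVID cutoff date of March 11, 2020". SAP Appendix III records that Amendment 2 added an analysis for "completed or discontinued patients prior to the COVID-19 pandemic onset, per the FDA feedback".

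The rule sets no condition on randomisation date or assessment date, and the SAP does not say which milestone counts as completing for this subset. SAP Section 3.0 describes screening "followed by 6 weeks of DB treatment followed by a 4-week safety follow-up" and times the primary analysis "after all participants have completed the 4-week safety follow-up or discontinued from the study". The schedule (SAP Table 3-2) puts Week 6 at Day 43 and the last visit, Visit 7, at Day 71, each with a window of 3 days either way. MADRS and CGI-S are last collected at Week 6. Protocol Section 8.4.4 lists only safety procedures for Visit 7.

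Section 16.1 also plans a comparison that does not depend on outcome: "sensitivity analyses for the primary and key secondary endpoints by pre-COVID and post-COVID randomized participants will be performed", divided at randomisation on or before versus after 11 March 2020.

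**The concern.** The two ways into the subset run on different clocks. A participant who drops out qualifies on the day of discontinuation. One who stays must first reach the completion milestone. Among people randomised too late to reach it before the cutoff, the subset keeps those who discontinued and deletes those who continued, with all their pre-cutoff visits. Membership is therefore decided after randomisation and can depend on response.

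The MMRM's missing-at-random assumption covers visits missing after dropout, given the scores already observed. It does not cover the removal of whole records because the participant stayed in the study. The analysis is meant to show the treatment effect free of pandemic influence. With this rule, a departure from the primary result could come partly from the selection, and information obtained before the pandemic is thrown away.

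**Working it through.** **The plan's own figures.** The SAP states no size or power for this subset. Its main power statement (SAP Section 13.0: 250 per arm, effect size 0.286, 15% dropout, correlation 0.58) gives an effective n per arm of 250 × [1 − 0.15 × (1 − 0.58²)] = 225.1. With truncated Hochberg at 0.9, leaving out the re-test step, simulation gives 83.7% for each dose and 91.1% for at least one, against the stated 83% and 90%. The 15% dropout rate is therefore used below as the plan's own input.

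**Dates.** Day d falls d − 1 days after Day 1, taken as the randomisation date. To be prior to 11 March, the milestone must fall by 10 March 2020.

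| Milestone | Days after randomisation | Latest randomisation date |
|---|---|---|
| Day 71, on schedule | 70 | 31 December 2019 |
| Day 71, 3 days early | 67 | 3 January 2020 |
| Day 43, on schedule | 42 | 28 January 2020 |
| Day 43, 3 days early | 39 | 31 January 2020 |
| Day 43, 3 days late | 45 | 25 January 2020 |

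On the Day 71 reading, on-schedule participants randomised 1 to 28 January have Week 6 by 10 March but Visit 7 on or after 11 March. Unless they leave before the cutoff, their Week 6 score is lost from this table. On the Day 43 reading no pre-cutoff Week 6 score is lost; continuing late enrollees lose only Week 1 to Week 4 scores.

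**Composition.** The documents give no accrual dates. Assume uniform accrual over A = 180 to 540 days before the cutoff, 15% dropout spread evenly over 42 days, and discontinuation dated when the participant leaves treatment. Protocol Section 8.8 supports that dating, since follow-up comes after discontinuation. Let L be 70 (Day 71) or 42 (Day 43).

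- Late share = L/A.
- Share of late enrollees kept, k: for L = 42, 0.15 × 0.5 = 0.075. For L = 70, 0.15 × (28/70 + 42/70 × 0.5) = 0.105. All are dropouts.
- Subset as a share of those randomised = (1 − L/A) + (L/A)k.
- Dropout share of the subset = [0.15(1 − L/A) + (L/A)k] / [(1 − L/A) + (L/A)k].
- Pre-cutoff Week 6 completers discarded (Day 71 only) = 28/(A − 42).

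For L = 70 and A = 180, the late share is 0.389, the subset is 0.611 + 0.389 × 0.105 = 0.652, and the dropout share is (0.0917 + 0.0408)/0.652 = 20.3%. Week 6 completers discarded are 28/138 = 20.3%.

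| | Day 71, A = 180 | Day 71, A = 540 | Day 43, A = 180 | Day 43, A = 540 |
|---|---|---|---|---|
| Late share | 38.9% | 13.0% | 23.3% | 7.8% |
| Kept in subset | 65.2% | 88.4% | 78.4% | 92.8% |
| Dropout share | 20.3% | 16.3% | 16.9% | 15.5% |
| Pre-cutoff Week 6 completers discarded | 20.3% | 5.6% | 0% | 0% |

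**Effect on the estimate.** An illustrative simulation took a true difference of about −2.57 MADRS points, missing-at-random dropout of about 16%, and accrual over 180 or 450 days. Week 6 means were estimated by sequential regression on earlier visits, standing in for the MMRM. Under the SAP's rule, arm means moved by about 0.02 to 0.25 points. When dropout depended on response alike in both arms, the difference barely moved: −2.565 in the full sample against −2.564 in the subset (180 days, Day 71). When it depended on response in one arm only, the largest shift was from −2.588 to −2.685, about 0.1 point. Two date-based rules gave −2.575 (a randomisation-date limit) and −2.582 (visits truncated at the cutoff) in that last setting, both within simulation error of the truth.

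**The case against.** The strongest reply is that little depends on this table. It is exploratory and carries no alpha and no decision rule. The excluded data stay in the primary analysis. The randomisation-date split is free of the selection, and Section 16.1 also summarises COVID-related missingness and remote assessment by visit. The subset is attributed to regulator feedback that cannot be read here. All of this stands and limits the weight of the point. It does not supply a replacement. The pre-COVID group of the randomisation-date split includes people randomised from 29 January to 11 March 2020, whose on-schedule Week 6 falls on or after the cutoff. Section 16.1 therefore has no analysis that is both confined to pre-pandemic data and free of selection on dropout.

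A reader might infer three stronger things, which the documents do not support:

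- **That 1 January 2020 is an exact line after which everyone kept is a dropout.** The cutoff wording is strict and visits may be 3 days early, so someone randomised on 2 or 3 January could still complete in time.
- **That loss of valid Week 6 scores is certain.** It depends on reading *completed* as Day 71. SAP Section 3.0 favours that reading, but SAP Section 6.0 reports discontinuation separately for the double-blind and follow-up periods, so a Day 43 reading is possible. Also, on the Day 71 reading, someone who leaves during follow-up before the cutoff is kept with a valid Week 6 score.
- **That the repeat is seriously biased because missing at random fails.** The principle is correct, but the shift in the treatment difference was near zero or about 0.1 point at most in the settings tried.

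**Conclusion.** The rule selects on post-randomisation status under either reading of *completed*, and the SAP leaves that word undefined. The cost is mainly precision and interpretability: 12% to 35% of participants randomised before the cutoff are excluded on the Day 71 reading (100% minus 88.4% and 65.2%), or 7% to 22% on the Day 43 reading (100% minus 92.8% and 78.4%), with a modest excess of dropouts among those kept. These ranges rest on assumed uniform accrual, 15% dropout spread evenly over six weeks, and discontinuation dated at leaving treatment; the true accrual pattern could move them. The bias figure comes from one illustrative simulation. The primary test, type I error and power are unaffected. This is a minor point, but the repair is inexpensive.

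**What to change.** Define the analysis by calendar date. Keep all mITT participants randomised before 11 March 2020, and fit the same MMRM using only MADRS and CGI-S assessments dated before 11 March 2020. Truncation at a fixed date does not depend on outcome, so the model can use the early visits of participants still on treatment. Those with no post-baseline visit before the cutoff contribute nothing.

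If a randomisation-date limit is preferred, set it so that Week 6 falls before the cutoff even with a visit 3 days late, that is, randomised by about 25 January 2020. A limit of 28 or 29 January would admit some Week 6 visits on or after 11 March.

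State whether *completed* means Visit 6 or Visit 7. Keep the present subset as a second table if the regulator requires it. The cost is one SAP sentence and one extra model run per endpoint.
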